4.1.6. PK Population (PKP)

The PK population (PKP) will include all randomized participants who received at least 1 dose of pridopidine and have at least 1 valid PK assessment. In this population, treatment will be assigned based upon the treatment participants actually received, regardless of the treatment to which they were randomized. This PKP will be used for all PK analyses.

5. GENERAL CONSIDERATIONS FOR DATA ANALYSES AND HANDLING

This section addresses the definitions, algorithms, imputations, and conventions that will apply to the analysis and handling of the data in general. Rules that are data specific will be addressed in the detailed discussions of individual sections below. This SAP and all Tables, Figures and Listings (TFLs) created will use U.S. spelling.

All changes to this SAP prior to locking the database and unblinding the study will be documented in an Addendum.

Any additional analyses performed or changes to the SAP and Addendums after unblinding the study will be described in the CSR under the section “Changes to Planned Analyses”.

5.1. General Summary Tables, Figures and Individual Participant Data Listing Considerations

Summary tables and listings (e.g., post text tables and individual participant data listings) are prepared according to ICH Guideline E3 will include a “footer” providing explanatory notes that indicate as a minimum (1) Date and time of output generation; (2) SAS program name, including the path that generates the output; (3) Any other output specific details that require further elaboration; (4) Page number in the format of Page X of Y.

Summary tables will include reference(s) to the participant data listing(s) to support the summary data. The data extraction date links the output to the archived database that is frozen to ensure the replication of the results.

For the Main Study, summary tables will display the 2 treatment groups, “Placebo” and “Pridopidine 45 mg bid”. An overall total column will be included, where appropriate.

Unless specified, row entries in summary tables are always displayed for every category even if no data exists for any participants (e.g., a row with all zeros will appear). The summary tables will clearly indicate the number of participants to which the data apply along with an indication for the number of participants with missing data.

If no data exist for any participants for a given Table or Listing, a text will be displayed to indicate why there is no data.

In summary tables for medications, medical conditions and AE verbatim (reported) terms are coded to preferred terms (PT) and body/organ systems are coded per standard dictionaries mentioned in Section 5.3.

All relevant data collected in the study will be presented in individual Participant Data Listings (unless agreed to with the agency to not create certain listings, e.g., Laboratory listings, which tend to be very large). All listings will include participant ID and treatment group. Where applicable, listings will also include visit number, visit date, and days relative to the initiation of treatment. Individual participant data listings, at a minimum, are sorted by Treatment, Participant ID, Assessment and Visit (Week), as applicable.

Relevant data derived for analyses will also be included with the raw data in the listings.

Supporting figures may be generated for key tables.

5.2. General Post Text Summary Table and Individual Participant Data Listing Format Considerations

The default convention is to number tables and listings using a decimal system to reflect main levels of unique tables and listings and sub-levels of replicate tables and listings with 2 or more numbers separated by 1 or more decimal digits (e.g., Table WW.XX.YY.ZZ).

1. The first level number will be consistent with the corresponding CSR appendix in which the tables or listings will appear. For example, the post-text tables usually occupy Appendix 14 and the individual participant data listings are in Appendix 16.2. All post-text tables should have a main number level 14 and listings should have a main number level 16.2. The disposition table is usually first in the first section of the report and will be numbered Table 14.1.
2. Participant accounting, final disposition and Baseline and demographic profile should appear as the second level number. Efficacy Tables would be next (14.2 series) followed by safety (Table 14.3 series).
3. The Table/Listings title should be unique, complete, accurate, and concise. The last line of the title should provide the analysis group being summarized (e.g., ITT population, mITT population, or safety population). If possible, the units of measurement for data contained in the table can appear in parentheses to conserve space in the body of the table. For example, the summary of vital signs title could read “Summary of Sitting and Standing Blood Pressure (mmHg) and Heart Rate (HR) (bpm).” Whether in the title, footnotes or body of a table or listing, units must always be specified for all appropriate data unless obvious.
4. If possible, variables being summarized, and statistics reported should appear in the left most column of a table. The next columns would be for the assessment, then the visits followed by treatment groups for the placebo, pridopidine, and (optional) all participants, respectively.
5. The definition of all relevant derived variables and decodes for coded data must appear on the Table and Listings. Tables and Listings should be self-contained and all-relevant information to review the Table or Listing will either be in the titles, column or row headers, or in footnotes.

5.3. Data Management

Data from the study will be entered into the EDC system TrialMaster version 5.0 (<https://www.anjusoftware.com/solutions/clinical-trials/trialmaster>), a validated electronic 21CFR Part 11 compliant EDC system. Data review, coding, and logic, range, cross-form, and consistency checks will be performed to ensure quality of the data⁵. AEs and medications will be coded using Medical Dictionary for Regulatory Activities (MedDRA) version 23.0 (or a later version if updated during the study) and the World Health Organization Drug Dictionary version March 2020, B3 (or a later version if updated during the study), respectively.

⁵ Guidance on the Management of Clinical Trials During the COVID-19 (coronavirus) Pandemic, Version 5, 2 Oct 2022. https://ec.europa.eu/health/sites/health/files/eudralex/vol-10/guidanceclinicaltrials_covid19_en.pdf

5.4. Data Presentation Conventions

Continuous variables (e.g., age) are summarized using descriptive statistics (the number of participants with available data, the mean, SD, first quartile (Q1), median, third quartile (Q3), minimum and maximum). Categorical variables (e.g., race) are summarized using counts and percentages. Percentages are calculated using the total participants per treatment group with available data (overall or within relevant subgroup when appropriate). Summaries for discrete variables will include frequencies and percentages. Unless obvious, denominators used for computation of percentages will be indicated in footnotes on tables.

The following conventions will be applied to all data presentations and summaries.

- For continuous variables, all mean, Q1 (25th percentile), median and Q3 (75th percentile) values are formatted to one more decimal place than the measured value. SD values are formatted to two more decimal places than the measured value. Minimum and maximum values are presented with the same number of decimal places as the measured value. This rule may be modified to fit data in a given table as long as the data displays relevant decimal places for interpretation of results.
- For categorical variables, the number and percentage of responses are presented in the form XX (XX.X%) where the percentage is in the parentheses and will be rounded to one decimal place.
- Date variables are formatted as DDMMYYYY for presentation. Time is formatted in military time as HH:MM for presentation.
- Wherever possible, data will be decimal-centered, or left aligned as appropriate to best display the data and column headers. Parentheses will also be aligned appropriately for best display. This will be detailed in the mock shells.
- P-values, if applicable, will be presented to 4 decimal places. If the p-value is less than 0.001 then it will be presented as <0.001. If the rounded result is a value of 1.000, it will be displayed as >0.999.
- Summaries of clinically significant abnormal values will include all post-baseline values (including scheduled, unscheduled, and ET visits).
- Unless otherwise stated, any statistical tests performed will use 2-sided tests at the 5% significance level.

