- f. After completing the Main Study EoS visit, eligible participants will have the option to continue for an Open-label Extension.
- g. When a participant discontinues study drug but continues to be followed in the study, they should first do ET visit and then continue with the follow-up off study treatment as scheduled.
- h. Visit window can be expanded any post Week 4 (V3) in-clinic visit window to ± 28 days; this applies to V4-8). The expansion of the in-clinic visit window is only in case of a global pandemic.
- i. To be done once, as early as Main Study Week 58, or at V7 (Main Study Week 65)/Main Study Week 72 (depending on when the participant is anticipated to transition to OLE).
- j. Inclusion/exclusion criteria should be met before Baseline visit.
- k. Safety laboratories should not be collected for participants who are off drug and remain in the study, unless there are abnormalities requiring follow-up.
- l. Serum pregnancy test will be performed at Screening. At Baseline visit, urine pregnancy test will be performed before first dose. Both test results must be known before first dosing. Urine pregnancy test will be performed at subsequent timepoints. An indeterminate or positive reading for the urine pregnancy test should be followed-up by a serum pregnancy test and the participant should be referred to a gynecologist if required. During the Treatment period, urine pregnancy tests will be performed monthly. Refer to Appendix 4 Section 10.4.
- m. Single ECG to assess eligibility.
- n. Baseline pre-dose assessment will include triplicate ECG administrations.
- o. Single ECG 1-2 hours post-dose.
- p. Single ECG pre-dose.
- q. Only for participants not continuing to Open-label Extension (single ECG). Participants continuing to OLE, will have triplicate ECG (pre-dose) at V8.
- r. Vital signs (body temperature, systolic and diastolic blood pressure, and heart rate) will be measured in a supine position after 5 minutes rest; thereafter, blood pressure should be measured again after standing for 2 minutes.
- s. For training purposes only.
- t. This information will be collected as part of the concomitant medication inquiry.
- u. Blood samples for plasma concentration of study drug will be collected 1-2 hours **after** dosing and **after** the ECG. PK samples should not be collected from participants who are off drug and remain in the study.
- v. Always collect blood after ECG is administered (not before).

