7.2. Discontinuation of Study Drug

In rare instances, it may be necessary for a participant to permanently discontinue (definitive discontinuation) study drug. A participant may discontinue study drug for reasons including but not limited to:

- AE
- Death
- Lost to follow-up
- Non-compliance with study drug
- Physician decision
- Pregnancy
- Protocol deviation
- Study terminated by Sponsor
- Withdrawal of consent by participant
- Loss of capability to consent

The reason for participant discontinuation from the study drug will be recorded in the eCRF.

Participants who are **discontinued from study drug** during the Main Study will be encouraged to continue their participation in the study and perform all the scheduled visits and assessments, while off study drug. If participants are unable/unwilling to attend in-clinic visits, these visits can be replaced with virtual phone visits except for the following: Main Study Week 65, Week 78/EoS and ET visits. If a clinic visit is replaced by a virtual visit at Week 4, Week 26, Week 39, and Week 52, the UHDRS-TFC, clinical laboratories, and vital signs should not be assessed (refer to Appendix 10, Section 10.10). They will continue to be closely monitored by the Investigator and will be referred for psychiatric evaluation per the Investigator's medical judgment. Participants who are discontinued from study drug during the OLE will be withdrawn from the study and will be requested to return to an EoS visit.

See the SoA (Table 2 – Main Study, and Table 3 – OLE) for data to be collected at the time of study drug discontinuation and follow-up and for any further evaluations that need to be completed.

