5.5.7. Study Periods

End of Study Day for each participant

End of the Main Study Day (double-blind period) for a participant is defined as the Main Study EoS/ET Visit, or last follow-up safety visit or phone call in the Main Study. **End of OLE Day** for a given participant is defined as the last follow-up safety visit or phone call for final data collection in the OLE period.

A participant is considered as a **Week 65 Completer (Main Study Completer)** if he/she has completed the Week 65 Visit without discontinuing earlier, regardless of whether they were on or off study treatment at Week 65. As per the study design, these participants may have completed visits beyond Week 65.

Treatment periods

Main Study Treatment Period is defined as the period from the first dose to the End of the Main Study Day. **OLE Treatment Period** is defined as the period from 1 day after End of the Main Study Day to End of OLE Day.

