8. SAFETY ANALYSIS

8.1. General

The SP will be used for all safety analyses based on the actual treatment received. AEs and SAEs will be collected from the Screening visit through end of the study period. Safety analyses will be presented separately for the Main Study and OLE according to the set of data associated with the two portions of the study.

Safety assessments will be summarized and listed for all data collected at in-clinic or VV (planned or converted).

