8.4. Adverse Events

All AEs will be coded using MedDRA Version 23.0 (or a later version if updated during the study).

For statistical analysis, a TEAE is defined as an AE that occurs for the first time or worsens (as captured on the eCRF) on or after initiation of treatment in the corresponding analysis period (Main Study or OLE Treatment Period) EoS. Due to the short half-life of Pridopidine (10-12 hrs) AEs that started more than 14 days after end of treatment are not considered TEAEs.

The terms AEs and TEAEs are used interchangeably in this SAP and unless otherwise specified refer to TEAEs.

An overall summary will be presented by treatment groups that includes the number and percentage of participants who experienced at least one TEAE for the following categories: All TEAEs, serious TEAEs, TEAEs leading to study discontinuation, TEAEs leading to death, TEAEs based on maximal Severity, TEAEs leading to study drug withdrawal anytime during the study, TEAEs leading to study drug withdrawal during titration. When appropriate, a total column may appear as the last column.

Summaries will be presented for all TEAEs by SOC and PT for the following categories of TEAEs:

- TEAEs, severe TEAEs, Treatment-related TEAEs, Serious TEAEs (see below for more details), TEAEs potentially related to QT prolongation, (e.g., palpitations, dizziness, syncope, cardiac arrhythmias, and sudden death), TEAEs related to abuse potential (See Appendix 12.2 for the AE terms), TEAEs causing discontinuation from the study.

The above summaries will include the number of events as well as number and percentage of participants experiencing at least one TEAE in each SOC and PT. To count the number of participants with any TEAEs, a participant who experiences multiple TEAEs within the same SOC will be counted only once for that SOC (if the TEAEs are coded to the same PT). A participant who experiences multiple TEAEs coded to the same PT within the same SOC will be counted only once for that PT. The number and percentage of participants experiencing any TEAE will also be provided. All percentages will use the number of participants in the SP within that treatment group as the denominator. In the summaries SOCs will be sorted in descending order based on number of participants in Total column; PT within SOC will be sorted by descending number of participants in Total column.

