8.8.2. ECG Parameters Data Presentations

Change from Baseline values will be calculated for each participant and visit as the value at the visit (averaged if measurements are taken in triplicate as described above) subtracted by the average Baseline value.

ECG data summaries and listings will include the following:

- The numbers and percentages of participants with the following clinically potential significant values will be presented at Baseline and each post-baseline visit:
 - Absolute QTcF values >450 msec; >480 msec; >500 msec
 - Change from Baseline in QTcF >30 msec; >60 msec
 For HR, PR and QRS use below:
 - HR: decrease of HR from baseline >10 bpm resulting in HR <60 bpm
Increase of HR from baseline >15 bpm resulting in HR >100 bpm
 - PR: increase of PR from baseline >25% resulting in PR >200 ms
 - QRS: increase of QRS from baseline >25% resulting in QRS >100 ms

Data listing of these values together with Baseline value and change from Baseline will also be provided:

- The number of participants and percentages of ECG interpretation (Normal/Abnormal Not Clinically Significant, Abnormal Clinically Significant) as determined by the ECG Central Lab at each scheduled visit and time point as well as the shift table from Baseline to each post-baseline visit will be presented by treatment groups
- The number and % of participants with ECG alerts as determined by the ECG Central Lab will be presented by treatment groups
- Descriptive statistics and boxplots of quantitative 12-Lead ECG parameters (HR [bpm], QTcF [msec], QTcB [msec], QT [msec], PR [msec], QRS [msec] and RR [msec]) and changes from Baseline will be presented by scheduled visits, time point and treatment group
- Central ECG Review of abnormalities will be summarized.

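### By-visit and last-value ECG, vital-sign and C-SSRS summaries mix off-drug with on-drug values under a fixed arm label, with no on-treatment counterpart; the dilution is real but probably small

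*SAP*

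**What the plan says.** **Follow-up off drug.** Under Protocol 7.2, participants taken off drug in the Main Study are "encouraged to continue their participation in the study and perform all the scheduled visits and assessments, while off study drug". They may replace some clinic visits by phone, but not Week 65, Week 78/EoS or the ET visit. The footnotes to the Main Study Schedule of Activities (Protocol 1.3.1) release them from PK sampling and, with an exception, from laboratory tests: "Safety laboratories should not be collected for participants who are off drug and remain in the study, unless there are abnormalities requiring follow-up".

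**Period and label.** The Main Study Treatment Period "is defined as the period from the first dose to the End of the Main Study Day" (SAP 5.5.7), so it includes time after the last dose. SAP 4.1.5 gives each participant one actual-treatment label for the whole double-blind period.

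**Summaries.** SAP 8.1 states: "Safety assessments will be summarized and listed for all data collected at in-clinic or VV (planned or converted"). SAP 5.4 adds, for abnormal values: "Summaries of clinically significant abnormal values will include all post-baseline values (including scheduled, unscheduled, and ET visits"). SAP 5.8.4 has abnormality and shift tables show each participant's worst value, latest value and value at each scheduled visit. For ECG, SAP 8.8.2 says: "Change from Baseline values will be calculated for each participant and visit". SAP 8.9 treats C-SSRS in the same way. None of these sections sets a cut-off at the last dose.

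**The one cut-off.** SAP 8.4, citing a half-life of 10 to 12 hours, states: "AEs that started more than 14 days after end of treatment are not considered TEAEs".

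**The concern.** Once drug is stopped, three different rules apply. ECG, in-clinic vital signs and C-SSRS values keep entering the arm's tables with no limit. Adverse events lose treatment-emergent status after 14 days. Laboratory values continue only for participants already known to be abnormal. The short half-life that justified the adverse-event window was not applied to ECG, although QTcF prolongation is the known risk and Protocol 2.3.1 describes it as linear in exposure.

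Two displays are at stake. The by-visit tables at Weeks 65 and 78 can mix recovered ECGs with on-drug ECGs. The latest-value row can report a participant's recovery after a QT stop as a pridopidine result. The SAP does not ask for the number off drug at each visit, so a reader of the study report could not judge how much this matters.

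**Working it through.** **1. Where off-drug ECGs fall.** ECGs after Week 4 are scheduled at Weeks 26, 65 and 78 (Protocol Appendix 8).
- An off-drug participant may take Week 26 by phone (Protocol 7.2). Table 8 in Appendix 10 lists no ECG at converted visits, and its footnote withholds home nursing from off-drug participants.
- Week 65 cannot be converted.
- The Week 78 single ECG is for those not entering the OLE. Entry requires completing on treatment, so off-drug participants are in that group.
- A confirmed QT stop also triggers a recovery ECG after about 2 days. As an unscheduled value it enters abnormality and shift tables, but not the by-visit means (SAP 5.8.4).

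Off-drug ECGs can therefore concentrate at Weeks 65 and 78.

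**2. Residual drug.** With a half-life of 10 to 12 h, the fraction of parent drug left is 0.5^(hours/half-life).
- After 48 h: 0.5^(48/10) = 3.6% to 0.5^(48/12) = 6.25%.
- After 14 days (336 h): below 1e-8.
- Five half-lives: 50 to 60 h.

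The half-life of the metabolite TV45065 is not stated.

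**3. By-visit dilution.** Let f be the share of pridopidine-arm ECGs at a visit that are off drug, and E the drug effect in those still on drug. Assume no drug effect off drug, and otherwise the same mean change as placebo. Then the pooled effect is (1 - f) x E. The plan gives no f. The values below are assumptions, with E = 6.6 ms from Protocol 2.3.1.

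| f | Pooled effect (ms) | Loss (ms) |
|---|---|---|
| 2% | 6.47 | 0.13 |
| 5% | 6.27 | 0.33 |
| 10% | 5.94 | 0.66 |

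**4. By-visit categories.** The excess over background shrinks by the same factor. With an assumed SD of 12 ms for QTcF change, the proportion above 30 ms is 2.56% on drug and 0.62% off drug. At f = 5%, the pooled figure is 0.95 x 2.56 + 0.05 x 0.62 = 2.46%.

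**5. Worst-value and any-visit counts.** The maximum over all values is never below the maximum over on-drug values. Adding off-drug values can only leave these counts unchanged or raise them.

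**6. Laboratory values.** Assume 240 per arm, f = 5%, a 2% on-drug abnormality rate, and 15% of off-drug participants retested: 228 on drug and 240 x 0.05 x 0.15 = 1.8 retested. If the retests are still abnormal, the visit rate is (4.56 + 1.8)/229.8 = 2.77%. If they have normalised, it is 4.56/229.8 = 1.98%. The direction depends on recovery.

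**7. The 22.5% dropout figure.** SAP 3.3 uses it to inflate 372 to 372/0.775 = 480, which reproduces. It then describes that 22.5% as having imputed Week 65 data, that is, no Week 65 assessment. Such participants are not the off-drug but examined group, so 22.5% neither estimates nor bounds f.

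**The case against.** The plan already protects against the worst outcome. A reader might infer that a QTcF above 500 ms would be hidden by later recovery. It would not. It stays in the worst-value row (SAP 5.8.4), in the count at the visit where it occurred, in the listing and among the central-laboratory ECG alerts (SAP 8.8.2). A resulting stop also counts in the tolerability endpoint (SAP 3.2.8). This stands, and it confines the point to by-visit and last-value displays.

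All-data tables by arm are also a legitimate view, notably for suicidality after a psychiatric stop. On-treatment tables bring their own selection: once QT-sensitive participants leave, the on-drug mean describes those who tolerated drug, and the effect may still seem to fade. That argues against replacing the all-data tables, but not against adding a second set.

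The 6.6 ms input is not shown to apply at Week 65. The Week 4 ECG is 1 to 2 hours post-dose, while the Week 26, 65 and 78 ECGs are pre-dose, so timing alone could lower the later estimates. This stands. The proportional loss does not depend on 6.6 ms, but the millisecond figures do.

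Three other inferences go too far. Adverse-event collection does not stop at 14 days: Protocol 8.3.1 runs it to the last follow-up visit, and only the treatment-emergent label ends. Off-drug vital signs are not universal, since Protocol 7.2 omits them at converted visits. Laboratory bias is not necessarily upward: Protocol 8.2.4 has abnormal tests repeated until they resolve or are no longer clinically significant, and Protocol 2.3.1 reports that creatinine recovers after stopping.

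**Conclusion.** The point holds for by-visit and last-value displays of ECG, in-clinic vital signs and C-SSRS, chiefly the Week 65 and Week 78 ECGs and ECGs after a QT stop. These mix off-drug with on-drug values, and the SAP specifies no on-treatment counterpart. A reversible effect is reduced roughly in proportion to the off-drug share at the visit.

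The size is probably small. SAP 3.6.3.1 calls discontinuation low, and no count of participants off drug but still examined is given. If the share is 2% to 5%, which is an assumption, the loss is 2% to 5% of the effect, or 0.13 to 0.33 ms on a 6.6 ms effect. This rests on negligible drug effect once off drug, which the parent half-life supports but which is unverified for the metabolite.

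A reader might go further and conclude that the safety results as a whole are distorted, or that up to 22.5% of the QT effect is lost. The documents do not support either reading. Worst-value and any-visit counts are not lowered, the 22.5% measures something else, and the laboratory direction is open.

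**What to change.** In SAP 8.6 to 8.9, flag every ECG, vital-sign, laboratory and C-SSRS value as on or off treatment, using the last-dose date and a pre-specified analysis window. Fourteen days would match the adverse-event rule. A shorter window for ECG should be justified from the stated half-life and that of the metabolite.

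Add on-treatment by-visit, shift and last-value tables beside the all-data tables, and show the number off drug at each visit. Keep the all-data worst-value tables as they are.

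The cost is one derived flag, some SAP wording and extra tables. SAP 5.5.6 already takes the last-dose date from the End of Treatment page. Its wording covers participants continuing beyond Week 65, so it should be extended to everyone; SAP 8.2 already needs that date for exposure. The downside to state is that on-treatment means describe those who stayed on drug, with slightly fewer late observations. Nothing changes in participant management or data collection.
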